### **Inclusion Criteria:**

- Ages 18 or older;
- Ambulatory without limitations: has never been advised by a clinician that increasing low-intensity walking would be unsafe;
- Prescribed statin medication;
- Self-reported low levels of physical activity;
- Access to and capable of using a smart cellular phone;
- After 2-week run-in, objectively-verified low levels of physical activity as documented by a commercially available Fitbit device;
- English speaking.

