The sample will include individuals prescribed primary prevention statin therapy with self-reported low levels of physical activity. Participants will complete a 2-week baseline run-in period where PA levels will be measured using Fitbit wearable devices and levels of adherence to statin medications will be assessed using eCAP smart pill bottles. During the baseline period, data from the Fitbit wearable devices will be used to verify participant's level of objective sedentary behavior. Individuals who are non-adherent to the protocol will be excluded and will not be randomized to the intervention. Following baseline, we will randomize 42 participants into 14 cohorts of 3 participants each for the intervention period. During the intervention period, participants will receive a BCT intervention, the length of which varies between 1 and 10 weeks depending on the assigned dose of a multi-BCT intervention. Assignment to doses will utilize modified TiTE-CRM methodology to adjust the dose for each cohort based on the results from the previous cohort. Following the intervention, all participants will be assessed over a 2-week follow-up period which includes passive data collection from the activity monitor, answering surveys and use of eCAP smart pill bottles to track medication adherence.

All collected data will be stored in the REDCap program, which is a Northwell IRB and Research IT security approved application, housed on the Northwell IT approved server. The MED will be defined as the smallest BCT dose duration associated with 80% of participants having a successful PA increase between the run-in and the follow-up periods. Change in PA will be defined as the difference in average daily PA between the run-in and follow-up periods. We will also assess Mechanisms of Action (MoAs) to determine potential mediators of the BCT intervention on PA. As increasing

PA may change statin adherence [7, 8], we will utilize eCAP smart pill bottles to measure adherence to statin medications.

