## 8. NUMBER OF SUBJECTS

- *Indicate the total number of subjects to be accrued locally. If applicable, distinguish between the number of subjects who are expected to be pre-screened, enrolled (consent obtained), randomized and complete the research procedures.*
- *If your study includes different cohorts, include the total number of subjects in each cohort.*
- *If this is multisite study, include total number of subjects across all sites.*

For this research, we will enroll up to 100 participants, with the goal of randomizing 42 individuals to the study intervention (14 cohorts of 3).

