have previously been shown to be effective on increasing health behaviors: Goal Setting, Action Planning, Self-Monitoring, Feedback, and Prompts/Cues. *Goal setting* is setting a goal defined in terms of the behavior to be achieved. For example, an individual may set a goal to walk 6,000 steps per day. *Action planning* is detailing the plan of where, for how long, and at what time physical activity is going to be performed. This BCT involves encouraging one to decide to act or set a behavioral resolution by forming *detailed plans* that link the behavior to specific situational cues. For example, a participant can decide they will walk for 30 minutes on weekdays following breakfast. *Self-monitoring of behavior* is defined as monitoring and recording behavior. For example, a person can keep a record of when they walk and the number of steps walked. *Feedback on behavior* is defined as providing informative or evaluative feedback on the performance of the behavior. For example, a person may receive a text message informing them they walked 42,000 steps over the past week, an average of 6,000 steps per day. *Prompts/cues* is defined as introducing or defining environmental and social stimuli with the purpose of prompting or cueing behavior. For example, texting a patient 30 minutes prior to a scheduled time for walking is an example of this BCT.

Participants begin the trial with a 2-week run-in period during which their baseline levels of PA (assessed using a Fitbit device) and compliance with study protocol will be assessed. Participants will also complete one questionnaire at the end of their baseline period to assess MoAs.

*Mechanisms of action (MoAs)*: This study will assess 5 potential MoAs by which BCTs may influence physical activity (walking) behavior. All MoA measures will be assessed bi-weekly (if applicable according to BCT package) via one electronic survey presented using RedCap

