## 12. STATISTICAL ANALYSIS

- *Describe how your data will be used to test the hypotheses.*
- *State clearly what variables will be tested and what statistical tests will be used.*
- *Include sample size calculations.*
- *If this is a pilot study, state which variables will be examined for hypothesis generation in later studies.*

Analysis for the Primary Aim: The minimum effective dose (MED) will be defined as the smallest BCT dose duration associated with a successful PA increase (defined as an average increase of 2,000 steps per day) between the 2-week run-in and 2-week follow-up periods in at least 80% of participants. The MED will be estimated based on the modified TiTE-CRM, which is an adaptive model-based, dose-finding design for estimating the maximum tolerated dose in pharmacologic agents. In this study, we will adapt the TiTE-CRM for the purpose of MED estimation. Briefly, the TiTE-CRM operates as follows during a study. Participants will be enrolled in cohorts of 3. The first cohort will be given a BCT intervention with a duration of 5 weeks. Subsequent cohorts will be given a BCT intervention duration (from 1-week to 10-week) based on the updated MED estimate according to the modified TiTE-CRM model and data from the previously enrolled participants. The process will continue until we reach a total of 42 participants (14 cohorts) randomized to the intervention. Once the study has completed enrollment, we will identify which dose of the BCT intervention (in weeks) is associated with  $\geq 80\%$  of participants achieving the goal of an average of 2,000 steps per day increase between the baseline and follow-up periods. Means and standard deviations of step scores for baseline versus behavioral change strategy treatment period will be visualized using a column graph. The statistical significance of differences will be adjusted for time interval. The effects of treatment on number of steps will be assessed using generalized linear mixed models (GLMM). This model will account for possible autocorrelation and linear trends between steps across time.

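### The 2-week Fitbit run-in both screens for low activity and serves as the baseline for the 2,000-step success rule, so a binding screen inflates observed success through regression to the mean, by an amount the plan leaves open

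*Combined protocol and SAP*

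**What the plan says.** **Screening use.** Section 7 (Inclusion Criteria) requires "After 2-week run-in, objectively-verified low levels of physical activity as documented by a commercially available Fitbit device". Section 2 says the same: "During the baseline period, data from the Fitbit wearable devices will be used to verify participant's level of objective sedentary behavior". Neither gives a step cut-off. Self-reported low activity is a separate criterion, applied before the run-in.

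**Baseline use.** Section 2: "Change in PA will be defined as the difference in average daily PA between the run-in and follow-up periods". Section 11 describes the run-in as the period in which "their baseline levels of PA (assessed using a Fitbit device) and compliance with study protocol will be assessed". Section 12 makes success binary, "defined as an average increase of 2,000 steps per day", and defines the MED as the shortest duration giving success "between the 2-week run-in and 2-week follow-up periods in at least 80% of participants".

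**Numbers.** Section 8: "we will enroll up to 100 participants, with the goal of randomizing 42 individuals". Section 12 calibrates the model to select a duration with 75%-85% success. It sizes the trial (n = 42) for a 60% probability of correct selection (PCS) under a logistic curve with slope 0.69 (OR 2).

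**What is absent.** No untreated or zero-duration arm, second baseline or correction for regression to the mean is described. The mixed model in section 12 allows for autocorrelation and linear trends in steps, but it is not tied to the binary outcome used for dose finding.

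**The concern.** A 14-day step mean is a person's usual level plus chance variation. Admitting only people whose mean falls below a cut-off keeps too many whose fortnight was unusually quiet. Subtracting that same mean from the follow-up mean then credits their natural return as gain. Everyone assigned a duration has passed the screen, so the inflation applies at every duration and moves the whole success curve up. The MED is the trial's main result and is read from that curve. An upward shift favours a shorter duration than the same rule would select with a baseline not used for screening.

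**Working it through.** **1. The plan's own figure.** I simulated a one-parameter continual reassessment design on the failure scale (target 0.20): 10 durations, start at week 5, 14 cohorts of 3, half-width 0.05, and a true OR of 2 per week with exactly 80% success at the true MED. Three choices are assumptions because the plan does not state them: slope per week, prior variance 1.34 and complete outcomes. PCS is 0.61 averaged over true MEDs at weeks 2-9, and 0.64 over all ten positions. The stated 60% is reproduced to within these choices.

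**2. Size of the regression effect.** The plan gives no step variances, so I assumed an SD of 2-week mean steps of 1,500-3,500, a correlation between two 2-week means (ICC) of 0.7-0.9, an individual-response SD of 1,000, and 42%-90% passing. The 42% is 42/100 from section 8, used as an extreme. For pass fraction Φ(z):

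spurious gain = (1 − ICC) × SD × φ(z)/Φ(z)

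With SD 2,500 and ICC 0.8, (1 − ICC) × SD = 500. The week shift is the logit shift divided by 0.69.

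| Pass | φ/Φ | Gain (steps/day) | 80% reads | Logit shift | Weeks shorter |
|---|---|---|---|---|---|
| 42% | 0.931 | 465 | 86.9% | 0.50 | 0.72 |
| 70% | 0.497 | 248 | 84.0% | 0.27 | 0.39 |
| 90% | 0.195 | 97 | 81.7% | 0.11 | 0.16 |

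Here 80% means success with an independent 2-week baseline in the same people. Over the whole grid the gain is 29-977 steps/day, 80% reads 80.7%-89.2%, and the shift is 0.07-1.05 weeks. At 90% passing the shift is only 0.07-0.23 week.

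**3. Cross-check with person, week and day components.** Assume person SD 1,500-2,500, day SD d = 2,500-3,000, week SD w = 500-1,000 and adjacent-week correlation ρ = 0-0.5. The within-person variance of a 14-day mean is V = d²/14 + w²(1 + ρ)/2, and the gain is V/√(person SD² + V) × φ/Φ.
- Low corner (person SD 2,500, d 2,500, w 500, ρ 0, 90% pass): V = 446,429 + 125,000 = 571,429; total SD = 2,612; gain = 218.8 × 0.195 = 43.
- High corner (person SD 1,500, d 3,000, w 1,000, ρ 0.5, 42% pass): V = 642,857 + 750,000 = 1,392,857; total SD = 1,909; gain = 729.8 × 0.931 = 679.

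On these components the gain is therefore roughly 40-680 steps/day, and 80% reads about 81%-90%.

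**4. Effect on selection (true MED at weeks 3-9).**

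| Logit shift | PCS | Selected too short |
|---|---|---|
| 0 | 0.61 | 15% |
| 0.1 | 0.60 | 22% |
| 0.2 | 0.59 | 30% |
| 0.3 | 0.54 | 38% |
| 0.5 | 0.40 | 56% |
| 0.69 | 0.24 | 74% |

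A second simulation with a power model started at PCS 0.66 and gave 0.61 at a shift of 0.14, 0.56 at 0.20 and 0.50 at 0.30. The 60% is therefore lost from about 0.2-0.3 logits upward.

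**5. Noise-free scale.** Suppose that 80% of people have a true, error-free gain of at least 2,000 steps. Over the grid in step 2 (run at 42% and 90% passing), observed success is 61%-76% with a fresh baseline and 64%-80% with the screening run-in. Measurement noise pulls success down and regression to the mean partly restores it.

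**The case against.** **The screen may hardly bind.** The 100 in section 8 is a ceiling that also covers non-compliance and withdrawal, and self-report has already selected low-activity people. A reader might infer from 42 of 100 that the Fitbit screen removes more than half; the documents do not support that. This stands. It limits the size but does not remove the mechanism, and without a cut-off nobody can show that the screen is lenient.

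**The design's 60% may survive.** A reader might infer that the stated PCS is simply not met. At shifts up to about 0.14 logits both simulations hold about 60%, so the loss is conditional.

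**The net direction may differ.** A reader might infer that the selected duration is too short in absolute terms. Against noise-free change that is not established (step 5), and reactivity to a new Fitbit could raise run-in steps and act against the bias. The documents give no data on either. The claim holds against the protocol's own rule, which is defined on observed 2-week means, when it is given an independent baseline.

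**Splitting the run-in is not a free cure.** Screening on days 1-7 and taking baseline from days 8-14 leaves a noisier baseline. Under assumed SDs it moves success by about −0.2 to +0.05 logits. With person, day and week SDs of 2,500, 2,500 and 500 and 80% passing, the uncorrected shift is only +0.10, so the split can distort more than it removes. It also leaves some bias if adjacent weeks are correlated.

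**A model-based baseline is unstable early.** With about 7 run-in participants the estimated shrinkage factor has a 90% range of 0.37-0.92 around a true 0.83. This stands against using it for the sequential assignments, but not against using it once at the end.

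**This is a pilot** seeking a preliminary MED. That lowers the stakes, but the MED is still its main result.

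**Conclusion.** The double use of the run-in is explicit, and nothing in the plan corrects for it. If the low-activity screen binds, observed success is inflated relative to the same rule with an independent 2-week baseline, and the selected duration tends to be too short on that scale. The direction on that scale needs only a binding cut-off and chance variation in 2-week means. The size rests wholly on assumed variances and pass fractions. The central case (84.0% read as against 80%) uses 4 of the 5 points of upper tolerance in section 12, strict screening can exceed it, and a screen passing about 90% makes the problem minor. The documents support neither an unconditional failure of the 60% PCS nor a claim that the duration is too short for noise-free individual change. The point deserves correction because the remedy is cheap, with medium confidence about its practical size.

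**What to change.** Keep the 14-day run-in and the sequential assignments as planned. In section 12, pre-specify that the final MED is also estimated with a baseline corrected for regression to the mean. That baseline is each participant's predicted mean from a mixed model fitted to the daily run-in steps of everyone who entered the run-in, including those screened out. Report it beside the raw-baseline MED, and state that if the two differ the raw-baseline MED may be too short.

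Fitted to 53-100 run-in participants under assumed SDs, this baseline read about 80%-82% with independent weeks and 81%-85% with correlated weeks. It was always nearer 80% than the raw run-in.

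The cost is a little more analysis, a normality assumption, and incomplete correction if adjacent weeks are correlated. It needs no extra visits, devices or participants. Stating the activity cut-off and reporting how many fail it would let readers judge the size.

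Screening on days 1-7 with baseline on days 8-14 is an option only if simulation at the planned cut-off shows that its noisier baseline (about 2-4 points lower observed success) costs less than the bias it removes.

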### **Exclusion Criteria**

- Age less than 18 years;
- Non-ambulatory or unsafe/not recommended to participate in a walking program;
- Not prescribed statin medication;
- History of CVD;
- Inability to comply with study protocol during 2 week run-in;
- Does not speak English;
- Unavailable for follow-up;
- Cognitive impairment;
- Severe mental illness (e.g., bipolar disorder or schizophrenia);
- Pregnancy

## 8. NUMBER OF SUBJECTS

- *Indicate the total number of subjects to be accrued locally. If applicable, distinguish between the number of subjects who are expected to be pre-screened, enrolled (consent obtained), randomized and complete the research procedures.*
- *If your study includes different cohorts, include the total number of subjects in each cohort.*
- *If this is multisite study, include total number of subjects across all sites.*

For this research, we will enroll up to 100 participants, with the goal of randomizing 42 individuals to the study intervention (14 cohorts of 3).

## 9. STUDY TIMELINES

- *Describe the duration of an individuals participation in the study*
- *Describe the duration anticipated to enroll all study subjects*
- *The estimated date of study completion*

Participants in this research could remain on study for up to 14 weeks.

All participants will undergo a 2 week run-in period and will then be enrolled in cohorts of 3. The first cohort will be given BCT intervention with a duration of 5 weeks. Subsequent cohorts will be given a BCT intervention duration (from 1-week to 10-week) based on the updated MED estimate according to the modified TiTE-CRM model and data from the previously enrolled participants. The process will continue until we reach a total of 42 participants (14 cohorts) randomized to the intervention; see sample size justification below.

All participants will then undergo 2 weeks of observation. In summary, participation will be between 5– 14 weeks depending on BCT dose assignment.

## 10. ENDPOINTS

- *Describe the primary and secondary study endpoints*
- *Describe any primary or secondary safety endpoints*

This study is a pilot whose primary purpose is to identify the MED of a multi-component BCT intervention needed to increase PA among participants on primary

prevention statin therapy. Secondary endpoints include pooling trial results across all participants to assess the mediation of MoAs for BCTs on physical activity and to identify any potential benefit of BCTs on increasing statin adherence.

## 11. RESEARCH PROCEDURES

- *Include a detailed description of all procedures to be performed on the research subject and the schedule for each procedure.*
- *Include any screening procedures for eligibility and/or baseline diagnostic tests*
- *Include procedures being performed to monitor subjects for safety or minimize risks*
- *Include information about drug washout periods*
- *If drugs or biologics are being administered provide information on dosing and route of administration*
- *Clearly indicate which procedures are only being conducted for research purposes.*
- *If any specimens will be used for this research, explain whether they are being collected specifically for research purposes.*
- *Describe any source records that will be used to collect data about subjects*
- *Indicate the data to be collected, including long term follow-up*

Potential participants will be first linked to an authorization form, allowing the study team to collect PHI necessary for the study. Participants who authorize PHI collection will then be asked to provide demographic information needed to comply with NIA reporting requirements. This basic demographic information (including age, sex, race, and ethnicity) will be used by the study sponsor for the purpose of determining equity and representativeness in recruitment for clinical trials. This demographic information is collected prior to eligibility screening to ensure that the study is not excluding potential participant groups. Afterwards, participants will be directed to an electronic screening questionnaire administered via REDCap to determine their eligibility. If eligible, participants will be automatically allowed to review and sign an informed consent form. Those who have signed the informed consent form are encouraged to discuss study procedures and address any questions with a clinical research coordinator. Prior to receiving study devices, participants will read and sign a device allocation document letting them know which devices they may keep upon study completion and which devices should be returned to study staff. Both eligible and ineligible participants will be presented with a series of optional demographic questions. Asking these questions is required by the study sponsor (NIA) with the intention of improving equity and representativeness in clinical trial recruitment. The optional questions are presented regardless of eligibility to ensure that the study is not excluding potential participant groups. These demographic questions will be provided to the NIA, the study sponsor, as part of the continuing report process. Study staff will set up the eCAP device and assign it to participants as they are enrolled and consented. Participants who sign consent will then be asked to answer some demographic questions during onboarding and will be mailed a commercially available Fitbit device and eCAP smart pill bottle after onboarding is complete. Upon receiving the smart pill bottle, participants will fill the eCAP pill bottle using their existing statin prescription.

The intervention will utilize the modified TiTE-CRM design as well as 5 BCTs, which

have previously been shown to be effective on increasing health behaviors: Goal Setting, Action Planning, Self-Monitoring, Feedback, and Prompts/Cues. *Goal setting* is setting a goal defined in terms of the behavior to be achieved. For example, an individual may set a goal to walk 6,000 steps per day. *Action planning* is detailing the plan of where, for how long, and at what time physical activity is going to be performed. This BCT involves encouraging one to decide to act or set a behavioral resolution by forming *detailed plans* that link the behavior to specific situational cues. For example, a participant can decide they will walk for 30 minutes on weekdays following breakfast. *Self-monitoring of behavior* is defined as monitoring and recording behavior. For example, a person can keep a record of when they walk and the number of steps walked. *Feedback on behavior* is defined as providing informative or evaluative feedback on the performance of the behavior. For example, a person may receive a text message informing them they walked 42,000 steps over the past week, an average of 6,000 steps per day. *Prompts/cues* is defined as introducing or defining environmental and social stimuli with the purpose of prompting or cueing behavior. For example, texting a patient 30 minutes prior to a scheduled time for walking is an example of this BCT.

Participants begin the trial with a 2-week run-in period during which their baseline levels of PA (assessed using a Fitbit device) and compliance with study protocol will be assessed. Participants will also complete one questionnaire at the end of their baseline period to assess MoAs.

*Mechanisms of action (MoAs)*: This study will assess 5 potential MoAs by which BCTs may influence physical activity (walking) behavior. All MoA measures will be assessed bi-weekly (if applicable according to BCT package) via one electronic survey presented using RedCap

*Beliefs about capabilities / self-efficacy* for walking is defined as beliefs about one's ability to successfully perform a behavior. Beliefs about capabilities/self-efficacy will be assessed using the Self-Efficacy for Walking (SE-W) scale,[26] a 10-item measure assessing patient's capabilities to walk for durations of 5 to 50 minutes. Items are scored from 0 to 100%, with scores of 0% indicating participants are "not at all confident" they could walk for that duration and scores of 100% indicating the participants are "highly confident" they could walk that duration. Items are averaged to create a total score, with higher scores indicating higher levels of beliefs about capabilities/self-efficacy.

*Behavioral regulation/ intrinsic regulation* is defined as behavioral, cognitive, and/or emotional skills for managing or changing behavior. Behavioral regulation will be assessed using a 4-item measure assessing intrinsic regulation, a subscale of the Behavioral Regulations in Exercise Questionnaire Version 2 (BREQ-2) [27]. Items are scored on a 0 (Not true for me) to 4 (Very true for me) scale, and averaged to create a total score, with higher scores indicating greater behavioral regulation capability.

*Feedback processes/discrepancy in behavior* is defined as processes through which current behavior is compared against a particular standard. Feedback processes will be assessed with a single item measuring discrepancy in behavior adapted from

Curtin and colleagues [28]. The text of the measure is “How large is the difference between your current walking behavior and your goal concerning your walking?” The question is rated from 0 (Not at all different) to 7 (very different) with higher scores indicating greater levels of discrepancy in behavior.

*Motivation* is defined as processes relating to the impetus that gives purpose or direction to behavior, and operates at a conscious or unconscious level. Motivation will be assessed with a message stating “I feel motivated to walk each day.” Participants will rate this item on a scale of 0 (Not true at all) to 7 (Very true) with higher scores indicating higher levels of motivation.

*Environmental context and resources* is defined as aspects of a person’s situation or environment that discourage or encourage the behavior. This MoA will be assessed using a checklist of 7 potential barriers to physical activity identified by Steinhart and colleagues [29] Barriers are coded on a 1 (Not often at all) to 5 (Very often) scale, and averaged to create a total score, with higher scores indicating that the listed barriers had greater effects on walking.

Following completion of the 2-week run-in period, participants will receive a variable duration BCT intervention, and the length of the intervention is determined by utilization of the modified TiTE-CRM design. During the BCT intervention, participants will receive 5 daily BCTs via text message. Content of the text message will be specific for each BCT (e.g. a Goal Setting text message will encourage participants to develop a walking goal for the day). Initially, 3 participants will be treated at a moderate dose level, which is five weeks of the multi-BCT intervention to increase PA. Based on the calculated MED for the first cohort, subsequent cohorts will be administered a longer or shorter dose of the intervention. The BCT dose for each cohort will be determined by the study statistician based on the proportion of individuals in the prior cohort exhibiting the target behavior (in this case, a 2,000 step per day increase between baseline and follow-up periods). As the MED involves comparing PA levels between the run-in and follow-up periods, participants will not be assigned to subsequent cohorts unless all of the participants in the prior cohort have completed some of the intervention period. The treatment response for the prior cohort will be used to guide the dose administered to the subsequent cohort using modified TiTE-CRM methodology.

Following the completion of the intervention, all cohorts will be assessed for a 2 week follow-up period. Follow-up consists of wearing the activity monitor continuously, and use of electronic pill bottle to assess adherence. No interventions will be delivered during this period. At the end of the study, participants will be asked to complete the same questionnaire completed during baseline and the intervention phase as well as a satisfaction survey regarding the BCT intervention. Participants will also be reminded/instructed to return their eCAP smart pill bottle to the study team via addressed packaging included in their study materials.

